The procedure that is study related, and may not be routine in every center, is the confirming examination when ROP determined to need intervention has been identified. In most of the centers, general or pediatric ophthalmologists perform the initial and repeat examinations. If an infant is close to needing intervention or needs intervention, a retinal surgeon is normally consulted to evaluate and perform the treatment, if (s)he agrees. This surgeon's evaluation will constitute the confirming examination, and in those centers, is the usual practice. For those centers where a single ophthalmologist performs both regular examinations and treatment of severe ROP, a second examination from an independent examiner is required, or if this proves impossible in particular circumstances, posterior pole fundus photographs are obtained to enable later independent confirmation of the findings. (Photographs will not require evaluation in real time in order to avoid delaying intervention which is time sensitive.)

Eye examinations will begin by Week 31 PMA and continue every 1/2 to 3 weeks as indicated by the clinical findings until each eye has reached the Acute/Final ROP status (up to a maximum of 55 weeks PMA for study purposes). Results of the examinations are recorded on the study CRF for each eye separately and include the lowest zone not fully vascularized, the highest stage of ROP in that lowest zone, the highest stage in any zone, the presence or absence of Pre-plus Disease or Plus Disease, and whether or not the criteria for ETROP Type 1 ROP requiring intervention have been met.

Type 1 ROP is defined in each eye separately and is ROP meeting any of the following combination of findings:

in Zone II: Plus Disease, with any Stage 2 or Stage 3 ROP;

in Zone I: Plus Disease with any stage ROP;

or Stage 3 ROP, even without Plus Disease.

The infant has reached **Acute/Final ROP status** when either of the following eye outcomes is observed: (Based on the 2013 AAP/AAO/AAPOS Guidelines for the Detection of ROP requiring treatment).

Favorable Acute/Final ROP Status: when both eyes are either:

Fully vascularized to the ora serrata on a single examination

or the retinal vessels have grown into Zone III, observed on two sequential examinations, showing only immature vessels, regressing ROP or Stage 1 or Stage 2 ROP.

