or the vessels have unequivocally reached Zone III on one examination in an infant of 35 weeks PMA or older, if there has been no previous ROP in Zone I or Zone II, and this examination is not the only examination the infant has had.

or PMA has reached 50 weeks and there is no prethreshold or worse ROP present.

Prethreshold ROP =

in Zone II, Stage 3 ROP or

in Zone I, any stage ROP

Unfavorable Acute/Final ROP Status: when one or both eyes show any of the following findings/circumstances, confirmed by a second examiner (or documented by fundus photograph):

ETROP Type 1 ROP (see above)

ROP that has progressed to stages worse than ETROP Type 1 ROP, including classic CRYO-ROP threshold, or any degree of retinal detachment;

Note: MISSING OUTCOME: If an infant receives an intervention for ROP before meeting criteria for an Unfavorable outcome or does not have a confirming examination (or fundus photographs), the infant's outcome will be considered a missing outcome. Intervening prior to this point is a study protocol violation and will require completion of a Protocol violation form by the treating physician explaining the circumstances. Handling of missing and indeterminate outcomes for the publication and regulatory submission analyses are discussed in Section 8.1.4.

An infant who dies before reaching a favorable Acute/Final ROP status will be considered to have an unfavorable Acute/Final ROP outcome, since death is a competing outcome for severe ROP (Freemantle 2003).

For infants who reach an unfavorable ROP status, a confirmatory examination is the preferred approach for validating the outcome, (but if such an examination cannot be performed, fundus photography for later evaluation is required). Infants that receive intervention without a confirming examination (or photographs) will be categorized as having a missing outcome. The confirming examiner is normally the retinal surgeon who will perform the intervention, and must

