5.3.2.2 Secondary Variables

- BPD: NICHD Physiologic Definition: Requiring oxygen to maintain an oxygen saturation of at least 90% at 36 weeks PMA (Walsh 2004).
- BPD (Physiologic Definition) or Death from BPD prior to 37 weeks PMA, with cause of death certified by the Center PI that BPD is the primary cause, or a significant co-contributing cause of death.
- All cause death: defined as death from any cause following randomization. The primary, underlying cause of death will be certified by the Principal Investigator at each center who may also list co-contributing causes.
- Any ROP: defined as ROP of any severity that is observed on at least 2 examinations in either eye through the time that Acute/Final ROP status is reached. ROP that is observed on only 1 of multiple eye examinations will not be considered “any ROP”. An infant who has only 1 eye examination prior to death, and that examination shows any stage ROP, will be also be considered as having “any ROP”.
- Type 2 ROP through the time that Acute/Final ROP status is reached: defined as 1 or both eyes reaching Type 2 ROP (ETROP 2003), but not Type 1. Type 2 ROP is defined as: (ETROP 2003).
 - in Zone II: Stage 3 ROP without Plus Disease, or
 - in Zone I: Stage 1 or 2 ROP without Plus Disease
- Severe IVH: IVH Grades 3 or 4 on either side of the brain, or extensive PVL. IVH will be classified as described by Papile (Papile 1978). PVL will be graded by the characteristics of the periventricular white matter on ultrasound or MRI done between 4 to approximately 6 weeks after birth per usual care (Barkovich 2000) and/or porencephalic cyst.

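### The *any ROP* outcome has no severity override and an inconsistent death exception, so in uncommon cases an infant can have Type 2 or severe ROP without having *any ROP*

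*Protocol*

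**What the plan says.** Protocol section 5.3.2.2 (Secondary Variables) gives *any ROP* a rule, its converse and one exception.

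- Rule: "defined as ROP of any severity that is observed on at least 2 examinations in either eye through the time" at which final status is reached.
- Converse: "ROP that is observed on only 1 of multiple eye examinations will not be considered" as *any ROP*.
- Exception, which counts as *any ROP*: "An infant who has only 1 eye examination prior to death, and that examination shows any stage ROP".

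Type 2 ROP, in the same section, is "defined as 1 or both eyes reaching Type 2 ROP (ETROP 2003), but not Type 1". No number of examinations is attached to it.

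Protocol section 5.3.1.1.2 (Ophthalmologic Examinations) sets out how follow-up ends.

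- Unfavorable status needs confirmation of Type 1 or worse ROP by a second examiner. The section allows a substitute: "but if such an examination cannot be performed, fundus photography for later evaluation is required".
- Favorable status can be reached when vessels have grown into Zone III, "observed on two sequential examinations, showing only immature vessels, regressing ROP or Stage 1 or Stage 2 ROP".
- It can also be reached when "the vessels have unequivocally reached Zone III on one examination in an infant of 35 weeks PMA or older", provided there was no earlier ROP in Zone I or II and this was not the infant's only examination. ROP in Zone III at that visit is not excluded.

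Section 5.3.1.1.2 also says that repeat confirming visits are commonly held jointly by both examiners. Neither section says whether a joint visit, or the later reading of a photograph, is one examination, two or none for the *any ROP* count.

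**The concern.** A reader of the results will take *any ROP* to contain Type 2 and severe ROP. As written it does not. The two more serious outcomes can be met on one examination, while the mildest needs two. An infant can therefore be a case for severe or Type 2 ROP and a non-case for *any ROP*.

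The death exception points the same way. It accepts that an infant who has died cannot be looked at again, but only when there was a single examination. An infant with an earlier clean examination and ROP at the last one is in the same position and is coded the other way.

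At stake is the coherence of a named secondary outcome. It is not a side issue clinically: section 3.1 names prevention of severe ROP, or even of any ROP, as the research goal. Classification also depends partly on events after randomization, namely death and missed visits; section 8.1.4 says families often miss appointments after discharge.

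**Working it through.** **Step 1. Trace each route against the rule.** The inputs are the definitions in sections 5.3.2.2 and 5.3.1.1.2 and the re-examination intervals in section 5.3.1.1.1.

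| Sequence | Other status | Examinations showing ROP | *Any ROP* as written |
|---|---|---|---|
| Clean examinations, then Type 1, then a separate confirming examination | Severe | 2 | Yes |
| Clean examinations, then Type 1 documented by photograph only | Severe | 1, unless the photograph counts | No |
| Type 2, follow-up continues, normally seen again within about a week | Type 2 | 2 or more | Yes |
| Type 2 first seen at the last of several examinations before death or loss | Type 2 | 1 | No |
| One examination, ROP present, then death | – | 1 | Yes, by exception |
| Two or more examinations, ROP at the last only, then death | – | 1 | No |
| Zone III immature vessels, then Stage 1 in Zone III at the next examination | Favorable | 1 | No |
| An earlier clean examination; then, at 35 weeks PMA or older, first Zone III examination shows Stage 1 | Favorable | 1 | No |

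Rows 2 and 4 are the contradictions between outcomes. Rows 5 and 6 are the contradiction within the death exception. Rows 7 and 8 are mild ROP for which follow-up closes on the first sighting.

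Type 2 ROP does not itself end follow-up. Section 5.3.1.1.1 has Zone I ROP, or Stage 2–3 in Zone II, re-examined in a week or less. Section 5.3.1.1.2 withholds the 50-week favorable rule while prethreshold ROP is present. Row 4 therefore normally needs death or loss soon after the first sighting.

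**Step 2. Reproduce the planning figures.** Section 8.2, Table 9 uses an effective 1672 infants, so n = 836 per arm. With two-sided α = 0.05 and pooled variance under the null,

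power = Φ{ [ |p1 − p2|·√n − 1.96·√(2·p̄·(1 − p̄)) ] / √( p1(1 − p1) + p2(1 − p2) ) }, where p̄ = (p1 + p2)/2.

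- Type 2, reduction, 0.25 against 0.175: (0.075 × 28.914 − 1.96 × 0.5785)/0.5761 = 1.796, power 0.964 (stated 0.96).
- Type 2, increase, 0.25 against 0.325: power 0.924 (stated 0.92).
- *Any ROP*, 0.65 against 0.455 or 0.845: power 1.00 both ways (stated 1.00 and 1.00).

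**Step 3. Stress the *any ROP* row.** The protocol gives no rate of single-sighting ROP, so the fractions below are assumptions. They are applied equally to both arms and treat 0.65 as the rate before any cases are missed. Observed prevalence is 0.65 × (1 − fraction missed).

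| Fraction missed | Observed prevalence | Power, 30% reduction | Power, 10% reduction (illustrative) |
|---|---|---|---|
| 0% | 0.65 | 1.00 | 0.78 |
| 5% | 0.6175 | 1.00 | 0.73 |
| 10% | 0.585 | 1.00 | 0.67 |
| 20% | 0.52 | 1.00 | 0.57 |

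The Table 9 entry does not move. Power would fall only for an effect smaller than the one planned for.

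**Step 4. Sample size.** Section 8.2 builds it on the primary outcome (0.30, with an absolute reduction of 0.07) and on losses: 1672/0.95 = 1760. *Any ROP* does not enter.

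**The case against.** The best case for the plan is that the two-examination rule is deliberate. The section states the rule, its converse and an exception, which reads as a considered guard against one-off mild findings. Nothing promises that the ROP outcomes nest; Type 2 is itself defined to exclude Type 1.

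The contradictory sequences are also uncommon. A second examination of severe ROP is the default, the surgeon must examine before intervening, and photographs are a fallback. Section 3.3.2.2 says 90% of unfavorable outcomes occur while infants are still in hospital. Type 2-level ROP is looked at again within about a week. Section 5.6 says ROP that will develop is normally manifest by 34 weeks PMA, which argues against much new ROP at a closing examination. Section 8.2 makes the secondary outcomes exploratory.

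All of that stands as an argument about frequency and weight. It also justifies keeping the rule for mild ROP. It does not justify coding an eye with Type 1 or Type 2 ROP as having no ROP: a guard against doubtful mild findings has no purpose there. Nor does it explain why one extra clean examination before death should turn a case into a non-case.

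Two stronger readings are tempting. One is that the schedule often leaves no chance of a second look, so that a sizeable number of infants is miscoded. The protocol gives no rate, and its intervals and confirmation rules point the other way for severe and Type 2 ROP. The planning value of 0.65 may also already reflect the two-examination definition, so a count of missed cases cannot be built on it. The other is that inositol, by bringing eyes to Zone III sooner, would lower *any ROP* without preventing ROP. Differential misclassification is possible in principle, but nothing in the protocol shows it, and the trial is double-masked with one examination schedule for both arms.

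**Conclusion.** The definition is wrong as written, with low impact. Read literally, it excludes photograph-only Type 1 ROP after clean examinations, and Type 2 ROP first seen at the last of several examinations before death or loss. It also treats infants who die differently according to whether an earlier clean examination took place. Mild Stage 1–2 ROP first seen at the examination giving favorable status is excluded too, but that is a trade-off against the two-examination rule, not a contradiction.

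The number of infants affected cannot be derived from the protocol. The primary outcome, the sample size of 1760 and the Table 9 power are unaffected. The conclusion assumes that a photograph reading is not itself counted as an examination, which the text leaves open, and that Type 2 ROP seen once is enough, since no number is attached to it.

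**What to change.** Amend the *any ROP* entry in section 5.3.2.2 as follows.

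1. Keep the requirement of two examinations for ROP milder than Type 2.
2. Add that an eye meeting Type 1 or Type 2 criteria at any examination makes the infant a case of *any ROP*.
3. Extend the death exception to ROP at the last examination before death, however many examinations came before.
4. State whether a confirming examination, a joint visit and a photographic evaluation each count as an examination.
5. Report mild ROP first seen at the closing examination as a sensitivity analysis, outside the main definition. In the main definition, a single mild sighting would count at the last visit but not at an earlier one, which would add a new dependence on follow-up.

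The cost is a few sentences and a re-derived variable. Section 5.3.1.1.2 already has zone, stage, plus disease and Type 1 status recorded for each eye at each examination, and no clinical procedure changes. The downside is that a few single mild findings before death will count as cases.

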5.3.3 Safety Variables

The safety variables will be the occurrence of adverse events and serious adverse events, in addition to the clinical diagnoses outlined below. These safety variables are described in detail in the MOP and recorded prospectively on the adverse event CRF. The grading of severity is guided by a Neonatal Toxicity Table (see the INS-3-06 case report form and Toxicity Table in the MOP).

5.3.3.1 Additional Clinical Outcomes Monitored for Safety

Unless otherwise specified, data collection for other common complications of prematurity is through the time of NRN “status”, i.e., the first occurring of: discharge home, death, transfer, or 120 days following birth. These include:

- Occurrence of necrotizing enterocolitis (NEC): Stage II or worse, whether treated (medically or surgically) and if the infant survived (modified Bell’s classification [Walsh 1986]).
- Isolated gastrointestinal perforation judged not to be due to NEC.
- Late onset sepsis: culture positive septicemia/bacteremia (≥ 72 hours of age) treated with antibiotics for ≥ 5 days or died before treatment was completed.
- Occurrence of clinically significant patent ductus arteriosus (PDA), and if received intervention with prostaglandin inhibitors, and/or surgery. This does not include prophylactic Indomethacin or Ibuprofen administered without the diagnosis of clinically significant PDA.
- Seizures treated with an anticonvulsant for >72 hours
- Total days on parenteral nutrition (including amino acids and/or lipids)
- Days on oxygen, days on ventilator
- If hearing screening was performed, did the infant fail in one or both ears (defined as never passing a hearing screening in one or both ears)

5.3.3.2 Variables Collected At the Long-Term Follow-up at 22-26 Months Corrected Age

Data collection for other common complications of prematurity obtained during long-term follow-up evaluation at 22-26 months will be conducted using the separate NICHD-NRN Follow-up Protocol. These data include:

- Neurodevelopment at 22-26 months corrected age (i.e., 22-26 months past due date) using the Bayley Scales of Infant Development III.
- Vision loss as diagnosed by an ophthalmologist as legally blind, and subdivided into “ophthalmic origin”, or “not ophthalmic origin” (i.e., cortical blindness is non-ophthalmic in origin and indicates that there is no retinal detachment or other abnormal fundus or ocular finding, except optic atrophy. Such cases will be considered central [neurologic] in origin.)
- Hearing loss requiring that hearing aids be prescribed.

- Cerebral palsy by severity category (absent/mild/moderate/severe).
- Overall health status per recall from the parent/guardian (including survival, re-hospitalizations, surgeries, ongoing medications, and chronic illnesses).
- An INS-2 specific additional data sheet will collect additional detail on ophthalmic re-hospitalization, surgeries, ongoing medications and chronic conditions (Subsequent ophthalmic surgery related to ROP, or other ophthalmic treatments, including glasses, contacts, scleral buckle, vitrectomy, cataract surgery, strabismus surgery, glaucoma treatment, etc.). This will form a final confirmation of the clinical findings and sequelae of ROP in each child following discharge. To facilitate collecting this information from outpatient ophthalmology visits (anticipated in all infants, and to involve serious medical issues in about 20%), explicit consent to obtain outpatient office records or hospital records will be included in the consent form.

5.4 Removal of Subjects from Therapy or Assessment

5.4.1 Discontinuation of Individual Subjects

Parents or legal guardians can elect to withdraw their infant(s) from the study at any time without compromise to the infants' care. Infants will be withdrawn from the study immediately if the Investigator believes it to be in the best interest of the subject. Infants who are prematurely discontinued from the study are not to be replaced, and their data will be included in the final analyses up to the point when or if parents withdraw permission to collect further data. Parents may withdraw an infant from the study treatment and also permit continued data collection (i.e., safety and outcome measures).

5.4.2 Discontinuation of Entire Study

NICHD may terminate this study prematurely, either in its entirety or at any study center, for reasonable cause by written notice to each center's Principal Investigator (or direct communication if urgent). Advance notice is not required if the study is stopped due to safety concerns. If NICHD terminates the study for safety reasons, NICHD will immediately notify the Investigators by telephone and subsequently provide written instructions for study termination.

5.5 Treatments

5.5.1 Treatments Administered

Within 12-72 hours of birth, all eligible subjects will begin treatment with 80 mg inositol/kg/day or placebo, according to individual randomization. Study drug will be administered daily and continue until the earliest of 34 weeks PMA, 10 weeks chronologic age, or the time of discharge. Study medication will be administered IV until enteral feeds reach 120ml/kg/day (or sooner if

the infant is no longer receiving IV fluids), at which time the same dose and formulation will be administered enterally.

Inositol: myo-Inositol 5% Injection is an isotonic, preservative-free, sterile 5% solution of myo-inositol in water containing 0.5 gm sodium chloride per liter (8.55mM), pH 6.5-7.5. It is administered via IV infusion using syringe pump over 15-30 minutes twice per day at 12-hour intervals at a dose of 80 mg inositol/kg/day (40 mg inositol/kg/dose), which is equivalent to 1.6 mL/kg/day (0.80 mL/kg/dose).

Placebo: 5% dextrose (5% glucose) in sterile water (D5W pyrogen and preservative free) United States Pharmacopoeia (USP) for IV infusion. Placebo will be administered in the same dose (80 mg glucose/kg/day divided in 2 doses administered every 12 hours) and dispensed in the same manner as the inositol.

Study drug should be infused into a vein rather than an artery because safety for arterial infusion has not yet been tested. It can always be given with a small saline flush preceding and following its infusion into a vein while other infusions are held during the study drug infusion.

Administration through the port of a multi-lumen line is acceptable since there is no mixing of solutions until it reaches the blood stream. In addition, in vitro testing was conducted with commonly used continuous drug infusions (for this population) including various TPN solutions and the results show inositol to be physically compatible with these selected solutions. The study drug may be co-infused with these solutions. See the Investigator's Brochure for specific testing completed and a listing of compatible co-infusion solutions.

Conversion to Enteral Administration

Once the infant has advanced to established enteral feedings (120ml/kg/day, or sooner if IV fluids are discontinued), study drug will be administered enterally via feeding tube, or by usual oral medication methods if the infant no longer requires a feeding tube. The same dose and formulation compounded for IV administration will be used for enteral administration.

5.5.2 Identity of Investigational Product

Myo-Inositol 5% Injection will be provided by AN and supplied to each center by dedicated clinical supply services. Placebo (5% dextrose in water USP) will be provided by each individual center or site's pharmacy from commercial stock supply.

Myo-Inositol 5% Injection will be supplied to the centers in 5 mL single-use vials containing 3 mL of solution. Each vial will contain 150 mg inositol in 3 mL (50 mg/mL). The solution will be sterile, at neutral pH, pyrogen-free and preservative-free. Sodium chloride is also present in the solution; each daily dose (80 mg inositol/kg/day) will add 0.014 mEq/kg/day of sodium intake.

Each vial of myo-Inositol 5% Injection will be labeled with the manufacturer's name and address, study sponsor, protocol number, Investigational New Drug (IND) caution statement, drug identification including lot number and vial number, and storage conditions.

Unit doses of inositol and placebo will be prepared and dispensed from each site's pharmacy in delivery syringes labeled for the ordered mg/kg dose as "Inositol Study Drug YY.Y mg, 0.8 mL/kg, administered IV over 15-30 minutes, or given as an enteral slow bolus, if feeding." [Note: The exact format of labeling will be per the normal pharmacy procedures to minimize the chance of errors.]

Myo-Inositol 5% Injection must be stored at controlled room temperature (15-25°C). When loaded into delivery syringes under sterile conditions, the drug is stable for more than 72 hours when stored at 2-8°C, and more than 48 hours when stored at 25°C/60% relative humidity.

Investigational products are for investigational use only, and are to be used only within the context of this study. The study drug supplied for this study must be maintained under adequate security and stored under conditions specified on the label until dispensed for subject use, returned to NICHD or representative or destroyed per instructions from NICHD and according to local regulations.

